# 7.6.2 Analysis of Secondary Efficacy Variables

# 7.6.2.1 PFR at 6 Months

PFR at 6 months using Kaplan-Meier method, with 95% and 80% confidence intervals (CIs) by treatment arm will be presented. If the Lower Confidence Limit of the 80% CI is greater than the assumed unaccepted PFR rate of 25%, it would serve as a signal that PFR at 6 months is higher than 25%.

# 7.6.2.2 Immune response and histologic and molecular tissue changes in tumor tissue or peripheral blood

Baseline and post treatment anti-NY-ESO-1 immune response and histologic and molecular changes in peripheral blood and tumor tissue and their association with clinical outcomes will be explored. Pre and post dosing antibody and T cell (+ vs -) will be summarized. In addition, a relationship between an induced anti-NY-ESO-1 immune response as well as tumor tissue changes during study treatment and clinical outcomes will be evaluated using peripheral blood and tumor tissue biopsies collected during study treatment at select sites. Association between Pre and post dosing antibody and T cell (+ vs -) and clinical outcome (PFS, OS) will be explored. Stepwise Cox regression analysis will be explored to investigator prognostic baseline factors associated with clinical outcome (OS, PFS).

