
Statistical Analysis	
Endpoints
 
Primary
 
The primary endpoints are the following:
 
• OS and PFS 
Secondary
 
The secondary endpoints include the following:
 
• Safety• Progression-free rate (PFR) at 6 months• TTNT• Immune response and histologic and molecular tissue changes in tumor tissue or peripheral blood• DMFS 
Exploratory
 
The exploratory endpoints are the following:
 
• TGR• PAR• To compare OS and PFS between treatment arms• ORR as assessed by RECIST (v1.1) modified to use irRC• DOR• CBR• Immune responses as measured by changes from baseline in anti-NY-ESO-1 immunity• Biomarkers• Quality of life 
Safety
 
The safety endpoints include the nature, frequency, and severity of AEs and MEOIs, laboratory abnormalities, and other safety assessments (including vital signs, LV305 persistence, physical examination findings, electrocardiograms [ECGs], etc.).
 
Statistical Analyses
 
Efficacy
 
The primary efficacy analysis will be the evaluation of OS and PFS using Kaplan-Meier methodology and will be performed on the ITT Population for each treatment arm. Kaplan-Meier plots and 95% confidence intervals (CIs) for 75%, 50% and 25% survival, if reached, will be provided for each treatment group.
 
A secondary efficacy analysis will be based on the proportion of patients that are progression-free at 6 months after start of study drug treatment (Day 0). Time-to-next-treatment and distant metastasis free survival will be compared between treatment arms based on a stratified log-rank test.
 
The immunologic efficacy in tumor tissue and peripheral blood will be evaluated by changes in concentration of immune cells (e.g., CD8+ T cells) and antibodies.

-----------------------------	---

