3.0 INTRODUCTION AND RATIONALE

[figure not shown]
The development of immunotherapeutic products that target specific tumors and appropriately harness the immune system to kill tumor cells is a promising approach for the treatment of human malignancies. Effective therapeutic immunization strategies for cancer require the induction of potent, stable, and self-renewing CD8 T cell populations directed against defined tumor-associated targets (TAAs). Human tumor cells express a variety of TAAs that are not expressed, or are minimally expressed, in normal tissues, and can serve as targets for the host cellular immune system to induce tumor destruction. The development of effective cancer therapeutic products may require both the induction of appropriate cellular immune responses and a mechanism to overcome evasion mechanisms.

NY-ESO-1 is a TAA and was one of the first cancer-testis (CT) antigens (Ag) described.¹ It is considered one of the top ten cancer Ags on the list for all cancers.² Normally, its expression is restricted to germ cells and is not seen in normal somatic tissues. However, NY-ESO-1 expression is seen in approximately 1/4 to 1/3 of melanoma, lung, esophageal, liver, gastric, prostate, ovarian, and bladder cancers. Up to 45% of melanomas and $\geq 80\%$ of sarcomas reported NY-ESO-1 expression.^{3,4,5,6} Thus, immunotherapeutics targeting NY-ESO-1 have the potential to be broadly applicable to a variety of cancer indications.

Immune Design (IMDZ) has developed a lentiviral vector (LV)-based immunotherapeutic platform called ZVex™ engineered to deliver Ag-encoding nucleic acids to dendritic cells (DCs) *in vivo*⁷ enabling direct Ag presentation to generate effective anti-tumor CD8 T cell responses. LV305 is a lentiviral vector that encodes NY-ESO-1 and is designed to generate NY-ESO-1-specific CD8 T-cell populations in patients where no such populations can be detected; thereby priming a T-cell mediated response. LV305 can also expand pre-existing NY-ESO-1-specific CD8 T-cell populations.⁶

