10.2.2.6.3 Immunogenicity

Descriptive statistics will be performed comparing the baseline and treatment administration peripheral blood NY-ESO-1-responsive T cells between the 2 treatment arms. Analyses will be performed to determine if there are any statistically significant changes from baseline values. Changes from baseline in serial anti-NY-ESO-1 antibodies will be expressed as geometric mean titers.

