10.2.2.6.4 Biomarkers

Descriptive statistics will be provided for biomarkers and treatments will be compared using analysis of variance (ANOVA), or non-parametric method when appropriate, of specific genes (e.g., T-cell receptors) and/or gene-networks (e.g., signaling of immune cells) and gene modules (e.g., sets of genes [typically 100-200]) that are up- or down-regulated in concert in certain conditions or disease states (e.g., infection, autoimmunity, etc.) will be performed. Data will be used to compare the baseline with responses post-treatment. Additionally, joint models of overall survival and longitudinal biomarkers may be explored.

10.2.2.6.5 Tumor Growth Rate, Progression Arrest Rate, Clinical Benefit Rate, and Quality of Life

Tumor growth rate and PAR will be explored between treatment arms. Additionally, the relationship between TGR and OS, and PAR and OS, may be explored.

Clinical benefit rate will be explored using methods similar to that described for ORR.

Quality of life as a composite endpoint (including but not limited to the following: while on study, the incidence of hospitalization, transfusions, and laboratory markers [eg. absolute neutrophil count, hemoglobin, and platelets]) will be explored.

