# 8 CHANGES FROM THE PROTOCOL SPECIFIED STATISTICAL ANALYSES

If discrepancies exist between the text of the statistical analysis as planned in the protocol, and the final SAP, a protocol amendment will not be issued, and the SAP will prevail.

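### The SAP specifies only a positive/negative summary of antibody and T-cell response and leaves out the protocol's titre and change-from-baseline analysis, so its summaries cannot separate a boosted response from an unchanged one in patients already positive at baseline

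*SAP*

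**What the plan says.** **SAP.** Section 7.6.2.2 gives one concrete summary for the antibody and T-cell part of the secondary immune endpoint: "Pre and post dosing antibody and T cell (+ vs -) will be summarized". The link to clinical outcome uses the same coding: "Association between Pre and post dosing antibody and T cell (+ vs -) and clinical outcome (PFS, OS) will be explored". Section 5.1.2.2 says only that the data will be collected. Section 2.3 keeps the immunogenicity objective, but the exploratory analyses in 7.6.3 contain no immunogenicity section. Titre, geometric mean and fold change appear nowhere in the SAP. No cutoff for positivity is given, and the induced response mentioned in 7.6.2.2 is not defined.

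**Protocol.** Section 10.2.2.6.3 is quantitative: "Changes from baseline in serial anti-NY-ESO-1 antibodies will be expressed as geometric mean titers", and "Analyses will be performed to determine if there are any statistically significant changes from baseline values". The synopsis says that immunologic efficacy "will be evaluated by changes in concentration of immune cells (e.g., CD8+ T cells) and antibodies". Sections 4.2.3 and 9.3.2 also describe immune response as change from baseline. For the secondary endpoint itself, section 10.2.2.4.2 says only that results are summarised by arm and names no scale.

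**Precedence.** Where the two documents differ, SAP section 8 says that "a protocol amendment will not be issued, and the SAP will prevail". That section lists no specific changes.

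**Expected effect.** Protocol 3.0 states that "LV305 can also expand pre-existing NY-ESO-1-specific CD8 T-cell populations". Protocol 7.2 describes the G305 doses as serving to enlarge the response primed by LV305.

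**The concern.** The trial adds a vaccine regimen to atezolizumab to raise NY-ESO-1 immunity. That can happen in two ways: a new response in a patient who had none, or growth of a response already present. A positive/negative table before and after dosing can show the first. For the second, a patient who starts positive can only stay positive or turn negative, so a large rise and no rise receive the same code.

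The association with PFS and OS inherits the problem. A combination-arm patient with a strongly boosted response and a control-arm patient with an unchanged baseline response look identical.

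What is at stake is the mechanistic evidence, that is, whether the combination raised immunity more than atezolizumab alone and by how much. The primary OS and PFS analyses are not affected.

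**Working it through.** **1. No plan figure to reproduce.** The documents give no power, cutoff, titre SD or baseline positivity for this endpoint. The first check is therefore a comparison of text.

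| Item | Protocol | SAP |
|---|---|---|
| Antibody | Geometric mean titres, change from baseline (10.2.2.6.3) | Positive/negative (7.6.2.2) |
| T cells | Comparison of baseline and on-treatment responsive T cells between arms (10.2.2.6.3); change in concentration (synopsis) | Positive/negative (7.6.2.2) |
| Assessment of change from baseline | Yes (10.2.2.6.3) | None named for immune data |
| Record of the change | – | None in section 8 |

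The SAP does specify change from baseline for laboratory values (7.8.4) and vital signs (7.8.5), so its absence for immune response is not a house style.

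**2. What the coding can show.** A pre/post table has four cells: −/−, −/+, +/− and +/+. A baseline-positive patient can fall only in +/+ or +/−. Any rise, whatever its size, lands in +/+, as does no change. This needs no numerical assumption.

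**3. Illustration of size.** All of the following are assumptions except the 40 per arm, which is from SAP section 4:
- baseline log10 titre is standard normal;
- change is log10(fold) plus normal noise with SD 0.3;
- the cutoff is set so that 20%, 40% or 60% are positive at baseline, that is 40 × 0.2 = 8, 40 × 0.4 = 16 and 40 × 0.6 = 24 patients per arm.

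The simulation used 200,000 draws per row. Each count is the simulated share still positive times the number positive at baseline.

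| True fold rise | Still + of 8 | Still + of 16 | Still + of 24 | Geometric mean fold rise recovered |
|---|---|---|---|---|
| 1 (none) | 8 × 0.859 = 6.9 | 16 × 0.894 = 14.3 | 24 × 0.920 = 22.1 | 1.0 |
| 2 | 8 × 0.971 = 7.8 | 16 × 0.977 = 15.6 | 24 × 0.985 = 23.6 | 2.0 |
| 4 | 8 × 0.997 = 8.0 | 16 × 0.998 = 16.0 | 24 × 0.998 = 24.0 | 4.0 |
| 10 | 8 × 1.000 = 8.0 | 16 × 1.000 = 16.0 | 24 × 1.000 = 24.0 | 10.0 |

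- 2-fold against 10-fold: 8 × 0.029 = 0.23, 16 × 0.023 = 0.37 and 24 × 0.015 = 0.36 patients.
- No rise against 10-fold: 8 × 0.141 = 1.1, 16 × 0.106 = 1.7 and 24 × 0.080 = 1.9 patients. All of this comes from fewer patients turning negative.

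On the titre scale the same patients return the true fold rise, as the last column shows.

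**The case against.** **The titre analysis is exploratory in the protocol and is not expressly withdrawn.** Both are true. Geometric mean titres sit in the exploratory section, and only the synopsis puts immunologic efficacy on a quantitative scale. The finding is therefore an unrecorded omission of a planned exploratory analysis, together with a coarse summary of a secondary endpoint. It is not the removal of a secondary titre analysis.

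**Magnitude may still be reported.** Protocol 9.4.11 puts immunological results on the CRF, and SAP 7.1 lists CRF data and summarises continuous variables by arm unless the SAP says otherwise. The table shells are in a companion document not available here. A reader might infer that boosting will be wholly invisible, and the documents do not support that: raw values may appear in listings. But 7.6.2.2 does specify another form of summary, 7.1 offers neither geometric means nor change from baseline, and a listing is not a between-arm analysis.

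**Baseline-positive patients still contribute.** They do, because they count in both proportions and can turn negative. The claim is limited to rises.

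**Stronger readings that do not hold:**
- A reader might attach an efficiency loss or a reduced effective sample size to the positive/negative coding. The usual result for a median split does not apply, because no cutoff is documented. A penalty for ignoring baseline does not fit a summary that shows both pre and post status.
- A reader might infer that the biomarker comparison in Protocol 10.2.2.6.4, where "treatments will be compared using analysis of variance (ANOVA), or non-parametric method when appropriate", ignores baseline. The same section also compares baseline with post-treatment data. It only fails to specify baseline adjustment.
- A reader might treat the two baseline blood draws as replicates to be averaged. The schedule notes and Protocol 9.4.11 say they are taken to secure yield, and two separate results are not promised.

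**Conclusion.** The point stands in this form. For antibody and T-cell response, the SAP's specified summaries, and the outcome association built on them, cannot distinguish a rise from no change in an individual who is already positive. At arm level the only trace is fewer patients turning negative. The protocol's quantitative analysis has been left out without a record, and the precedence clause favours the SAP.

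The structural part follows from the coding alone. The patient counts rest on the assumed normal titres, the SD of 0.3 log10 and baseline positivity of 20% to 60%. They also use 40 per arm, which may be too many because PBMC samples come only from trained sites.

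The histologic and molecular parts of the endpoint are not restricted to positive/negative and lie outside this point. Because between-arm comparisons are exploratory under SAP 7.9 and OS and PFS are untouched, this is a change that should be made. It does not threaten the main conclusions.

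**What to change.** In SAP 7.6.2.2:

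- Restore geometric mean titres and fold change from baseline by arm, and add quantitative T-cell change, at Days 42, 70 and 98.
- Analyse both on the log scale with the baseline value and disease type as covariates. Report between-arm geometric mean ratios with 95% CIs, labelled exploratory.
- State a rule for undetectable values. Log analysis needs one, and Protocol 3.0 anticipates patients with no detectable NY-ESO-1-specific CD8 T cells.
- Show results by baseline status (positive or negative).
- Keep the positive/negative summary as supportive, with a stated cutoff and a definition of an induced response.
- Record any remaining departure from the protocol in SAP section 8.

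The cost is SAP wording and a few extra tables. Blood for immune assays is already scheduled on these days in both arms. Site-restricted sampling may leave fewer than 40 patients per arm, so the number analysed should be shown with each estimate.

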# 7.6.2.3 Time to Next Treatment (TTNT)

TTNT will be analyzed using the same methods described for OS/PFS.

# 7.6.2.4 Distant Metastasis-Free Survival (DMFS)

DMFS will be analyzed using the same methods described for OS/PFS.

## 7.6.3 Exploratory Analyses

# 7.6.3.1 Tumor Growth Rate and Progression Arrest Rate

PD/SD at screening will be summarized.

Post treatment initiation, spider plot (% change and change from baseline in sum of longest diameter of target lesions) for all visits will be presented.

# 7.6.3.2 Overall Response Rate (ORR) and Duration of Response (DOR)

ORR will be estimated using the ITT set and EE set will be provided along with their corresponding 2-sided the 95% exact CI using Clopper-Pearson method. Best Overall Response (CR, PR, SD, PD and not evaluable) will be tabulated with 2-sided 95% CI in the same table.

ORR will be compared between treatment arms using a logistic regression. Logistic regression will be performed with the treatment arm and stratification factor of disease type as independent variables.

Lesion assessment (lesion type, organ site, evaluation method, diameter, lesion status and overall response) at each visit will be presented in a data listing.

Median DOR with the corresponding 95% CI will be estimated using the Kaplan-Meier method in each treatment arm. The Kaplan-Meier plots will be displayed.

DOR data will be presented in a data listing.

# 7.6.3.3 Clinical Benefit Rate (CBR) and Duration of Clinical Benefit

CBR and Duration of clinical benefit will be analyzed using the same methods described for ORR and DOR.

# 7.6.3.4 Time to New Lesion

Time to New Lesion will be analyzed using the same methods described for OS/PFS.

# 7.7 Subgroup Analysis

The following subgroups will be used for primary PFS and OS analysis in ITT and Efficacy set.

- Excluding safety run-in patients
- Patients with confirmed CR/PR/SD on study
- Patients with unconfirmed CR/PR/SD on study
- Patients with confirmed PD on study
- Type of Sarcoma (Myxoid/Round Cell Liposarcoma and Synovial Sarcoma)
- NY-ESO-1 (%) categories (1-<100, 100)
- NY-ESO-1 (%) categories (1-75, >75-99)
- Age (<48 Years, >=48 Years)
- Sex (Female, Male)
- Baseline ECOG (0, 1)
- Time from Diagnosis (<30.3 months, >= 30.3 months)
- Time from Diagnosis (<18.4 months, 18.4 <46.8 months, >= 46.8 months)
- Disease Status at Study Start (Locally Advanced, Metastatic)
- Metastatic Status (Relapsed/Recurrence of prior metastatic, Relapsed/Recurrence of prior locally advanced)
- Stage at Diagnosis (I/II/III, IV)
- Race (White, Other)
- Progression Status at Screening (SD, PD)
- Number of lines of prior chemotherapy (1, 2, >=3)
- Number of Target/Non-Target Lesions (<=3, >=4)
- Number of Target lesions (<=2, >=3)
- Patient with 1 prior line of chemotherapy and with response SD or better in prior therapy
- Synovial Sarcoma patient with 1 line of chemotherapy and with response SD or better in prior therapy

The below subgroups are defined for PFS analysis only.

- New target lesion on study (Yes, No)
- Total size of target lesion at baseline (0-15 mm, 16-50 mm, > 50 mm)
- Number of organs with target/non-target lesions at baseline (1, 2, >=3)
- Prior Anthracyclines Use (Yes, No)

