# 7.6.1 Analysis of Primary Efficacy Variables

# 7.6.1.1 Progression-Free Survival (PFS) and Overall Survival (OS)

PFS and OS analyses by treatment arm using Kaplan-Meier methodology based on the ITT set will be performed. Median with 95% CIs by treatment arm will be provided by treatment arm. The Kaplan-Meier plots will be displayed. The SAS code used to calculate the median (and 95% CI) and create the Kaplan-Meier plot is listed in Appendix 2.

As an exploratory analysis, PFS and OS between CMB305+atezolizumab arm vs. atezolizumab alone arm for all ITT patients will be compared. Hazard ratio, its corresponding 95% confidence interval (CI), and p-value (based on a 2-sided stratified log-rank test) from a Cox proportional hazards model stratified by disease type will be presented. Unstratified analysis will also be performed to estimate the hazard ratio and the corresponding 95% CIs and p-values. Since the sample size is not based upon a hypothesis to be tested regarding the differences in PFS between treatment arms, the statistical analyses to compare PFS and OS differences between treatment arms should be considered exploratory.

Exploratory analyses of OS at 6, 12, 18, and 24 months, and PFS at 3 and 12 months will also be assessed. The survival rate estimates between the two treatment arms will be compared using the following:

Z= difference in x-month survival rates / square root of sum of variance

where variance=square of survival standard error from Product Limit Estimate from SAS PROC LIFETEST, assuming independence of the two treatment arms, and the survival standard error for x-month is the same as the survival standard error at the event time prior to x-month if x-month is not an event time.

A forest plot of hazard ratios and their two-sided 95% confidence intervals will be presented for the subgroups defined in section 7.7 of this document, based on the ITT analysis set. The interaction p-value from Cox proportional hazards model will be also shown in the plot.

Progression-free survival and overall survival data will be presented in data listing.

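### SAP 7.6.1.1 plots between-arm hazard ratios for four SAP 7.7 subgroups that are defined by what happens after randomisation; these rows do not estimate a treatment effect

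*SAP*

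**What the plan says.** SAP 7.6.1.1 defines one hazard ratio, CMB305 plus atezolizumab against atezolizumab alone. It then says that a forest plot of hazard ratios with 95% confidence intervals "will be presented for the subgroups defined in section 7.7 of this document", in the ITT set, and adds: "The interaction p-value from Cox proportional hazards model will be also shown in the plot". No subgroup is exempted.

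SAP 7.7 mixes two kinds of group. Most are baseline features such as sarcoma type, age, sex and ECOG. Four are on-study outcomes:

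- "Patients with confirmed CR/PR/SD on study" (PFS and OS)
- "Patients with unconfirmed CR/PR/SD on study" (PFS and OS)
- "Patients with confirmed PD on study" (PFS and OS)
- "New target lesion on study (Yes, No", with two levels (PFS only)

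Neither section sets a landmark for these four or marks them as non-randomised. SAP 7.6.1.1 does say that "the statistical analyses to compare PFS and OS differences between treatment arms should be considered exploratory", and SAP 7.9 treats the p-values as descriptive.

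**The concern.** A subgroup hazard ratio keeps the protection of randomisation only if membership is fixed before treatment can act. Response, stable disease, progression and new lesions are outcomes. If the combination works, it moves patients between these groups. The patients left in, say, the progression group then differ between arms in ways that randomisation did not balance.

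For PFS the problem is sharper. Confirmed progression is the event, so that row contains only patients selected for having it. New lesions are close to the event as well, because under Protocol Appendices C and D new measurable lesions are added to the tumour burden from which progression is judged.

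The rows would stand in the same plot as valid baseline subgroups. A PFS benefit that is uniform across patients could look weak in one row and strong in another, and the new-lesion row could suggest an interaction that does not exist.

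**Working it through.** **1. Which items can carry an interaction p-value.** An interaction test needs at least two levels. Of the four on-study items, only new target lesion (Yes, No) has them. The other three are single groups. They are not complements of one another either, since a patient can have stable disease first and progress later. Some other items in the list are also single-level, for example "Excluding safety run-in patients". For these the p-value in SAP 7.6.1.1 is undefined.

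**2. Inputs for PFS.**
- SAP section 4: exponential PFS with medians of 3 and 5.2 months. The plan's 6-month rates reproduce: 2^(-6/3) = 25.0% and 2^(-6/5.2) = 44.9%.
- SAP 3.1: scans every 6 weeks for 12 months, then every 12 weeks; 40 patients per arm.
- Assumed: the combination arm has the 5.2-month median and the control arm has 3 months, and progression is dated to the next scan. Symptomatic deterioration and death before progression are not modelled.

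**3. Entry into the progression group.** The last scan inside 12 months is at week 48 (48 × 7/30.4375 = 11.04 months). The last inside 24 months is at week 96 (22.08 months).
- 12 months: 1 - 2^(-11.04/5.2) = 77%; 1 - 2^(-11.04/3) = 92%.
- 24 months: 1 - 2^(-22.08/5.2) = 95%; 1 - 2^(-22.08/3) = 99%.

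**4. PFS hazard ratio, simulated (400,000 patients, Cox model, Breslow ties).**

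| Cutoff | ITT | Confirmed progression group |
|---|---|---|
| 12 months | 0.62 | 0.80 |
| 24 months | 0.62 | 0.68 |
| 72nd death | 0.61-0.63 | 0.61-0.64 |

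The continuous-time value is 3/5.2 = 0.58; tied scan dates under Breslow move it to 0.62. With Efron ties the figures are 0.58 (ITT), 0.77 (12 months) and 0.64 (24 months).

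The 72-death row uses simulated 80-patient trials with assumed accrual over 12-24 months and assumed median survival after progression of 6-15 months. By then about 97-100% of each arm is in the progression group, so the group is nearly the whole ITT set.

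Against sampling error at 40 per arm:
- 12 months, 31 + 37 events: standard error sqrt(1/31 + 1/37) = 0.24; shift ln(0.80/0.615) = 0.26, about 1.1 standard errors.
- 24 months, 38 + 40 events: standard error 0.23; shift ln(0.682/0.619) = 0.10, about 0.4 standard errors.

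If treatment does not change PFS, the progression-group hazard ratio is 1.00.

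**5. New target lesion (PFS).** The documents give no rate, so this is a range.
- If 30-70% of progressions, equally in both arms, carry a new lesion and no other patient does: 0.80 (Yes) against 0.48-0.58 (No) at 12 months, and 0.68 against 0.53-0.60 at 24 months, with no true interaction. In simulated 80-patient trials the interaction p-value is below 0.05 in 6-21% (12 months) or 3-10% (24 months), against 2-4% for a random baseline subgroup.
- If 50% of progressions and 10-30% of other patients carry one: about 0.66-0.74 against 0.55-0.57 at 12 months, and 0.64-0.67 against 0.58-0.60 at 24 months.
- At 48 months, under either assumption: about 0.62 against 0.61.

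**6. OS.** Assume no treatment effect on OS, disease control of 55-65% against 50%, and a latent prognosis that drives both response and OS. The simulated hazard ratio is 1.01-1.22 in the response or stable-disease group and 1.02-1.28 in the progression group. If both arms have 50% disease control it is 0.99-1.01. For scale, 46 patients with 41 deaths split 23.4 and 18 give a standard error of sqrt(1/23.4 + 1/18) = 0.31. At a hazard ratio of 1.1 the 95% interval is 1.1 × exp(±1.96 × 0.31), about 0.6-2.0.

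**The case against.** The strongest reply is that nothing depends on these rows. The primary analysis is Kaplan-Meier by arm, the PFR signal in SAP 7.6.2.1 is per arm, and the comparisons are labelled exploratory. That stands, and it caps the severity. It does not answer the point, because such a label governs how much weight a p-value carries, while the problem here is bias in the estimate.

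A second reply concerns timing. Protocol 10.2 and 10.3 set the final analysis at 72 or more deaths, when almost everyone has progressed and the PFS distortion nearly vanishes. This also stands. A reader might take 0.80 as the expected distortion, but it belongs to a 12-month cutoff that neither document sets. It becomes relevant only through the clause that lets the Sponsor analyse sooner.

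Third, Protocol Appendix C says that a new lesion does not by itself define progression. Patients without progression can therefore fall in the Yes group, which shrinks the contrast, as step 5 shows.

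Fourth, SAP section 1 leaves the layout of displays to companion shells that are not available here. These might omit the rows, but the SAP text as written includes them.

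**Conclusion.** The point holds as a minor one. Followed literally, SAP 7.6.1.1 and 7.7 produce four sets of between-arm hazard ratios that do not estimate a treatment effect. This follows from the definitions of the groups and needs no simulation. The sizes do rest on assumptions: exponential PFS at the planning medians, scan-dated progression, assumed new-lesion rates, and an assumed link between prognosis and response. The PFS distortion matters mainly if the Sponsor analyses early. The OS distortion is modest against its interval.

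Three stronger readings are not supported:

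- That the trial's main conclusions are at risk. The primary estimates and the PFR rule do not use these rows.
- That all four items yield spurious interaction p-values. Only the new-lesion item has a defined one, and it is for PFS only.
- That SAP 7.6.2.2 builds in immortal-time bias when it relates post-dose antibody and T-cell status to PFS and OS. It says only that the association will be explored and does not specify an ever-positive analysis from randomisation. Protocol 10.2.2.6.4 also allows joint models of OS and longitudinal biomarkers. This is at most a request for clarification.

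**What to change.** In SAP 7.6.1.1 and 7.7:

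- Remove the four on-study items from the between-arm hazard-ratio forest plot and from the interaction tests.
- If outcome by response is of interest, show it descriptively, by arm, from a fixed landmark such as the week-12 scan, labelled as a non-randomised comparison.
- State that single-level items carry no interaction p-value.

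The cost is SAP wording and minor programming. No randomised comparison is lost, because none of the four rows is one.

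As an optional clarification in SAP 7.6.2.2: if post-dose immune status is related to PFS or OS, say that a landmark or a time-dependent covariate will be used. A Day-98 landmark for PFS has a price. At the planning medians, progression by the Day-84 scan removes 1 - 2^(-(84/30.4375)/5.2) = 31% to 1 - 2^(-(84/30.4375)/3) = 47% of patients. A time-dependent covariate avoids that loss.
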